5. TEST ARTICLE ALLOCATION AND MASKING

5.1. Test Article Allocation

The study lenses will be worn in a bilateral and random fashion using a 2×2 crossover design with 2 lens types and 2 periods. Using a computer-generated randomization scheme provided by the study biostatistician, each subject will randomly be assigned to one of two unique sequences (Test/Control or Control/Test). Randomization will be stratified by site.

Permuted block randomization will be used to avoid bias in the assignment of subjects to treatment, and to enhance the validity of statistical comparisons across treatment groups. Each block will contain two different lens trial sequences.

The order of lens wear will be based on the randomization scheme assigned to the study site. The study site will follow the randomization scheme provided and will complete enrollment according to the randomization list and will not pre-select or assign subjects.

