14.5. Primary Analysis

Primary efficacy analysis:

Overall quality of vision scores will be analyzed using a linear mixed model adjusting for baseline values as fixed covariates. The model will include the experimental design factors: sequence of lens wear, period, lens type, time point and interaction between lens and time point as fixed effects. The covariance between residual errors from the same subject across lens wearing periods/time point will be selected based on the finite-sample corrected Akaike's Information Criterion.⁶ Covariance structures considered may include: Homogenous compound symmetry (CS) and Unstructured covariance structure (UN). The structure that returns the lowest Akaike Information Criteria Corrected (AICC) will be selected as the structure that best fit the data.

Comparisons between the Test lens and Control lens at 2-week follow-up will be carried out using 95% confidence intervals constructed of least-square means (LSM) differences (Test minus Control) from the linear mixed model. The non-inferiority of the Test lens relative to the Control will be concluded if the lower confidence limit of LSM difference is above the non-inferiority margin -5. The superiority will be established if the lower confidence limit is above 0.

In all models, the Kenward and Roger method⁷ will be used for the calculation of the denominator of degrees of freedom.

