14.6. Secondary Analysis

Secondary efficacy analysis:

Binocular, high luminance, high contrast visual performance on logMAR scale will be analyzed using a linear mixed model to test for the difference between the study lens systems. Each model will include the experimental design factors: sequence of lens wear, lens wearing period, lens type, distance and the interaction between lens type and distance as fixed effects. Other baseline characteristics known of importance such as age, gender, and/or add power will be included as fixed covariates when appropriate. Site and subject nested in site will be included as random effects when appropriate. The covariance between residual errors from the same subject at the same distance across lens wearing periods will be selected based on the finite-sample corrected Akaike's Information Criterion.⁶ Covariance structures considered may include: Homogenous compound symmetry (CS) and Unstructured covariance structure (UN). The structure that returns the lowest Akaike Information Criteria Corrected (AICC) will be selected as the structure that best fit the data.

Comparisons between the Test lens and Control lens will be carried out using 95% confidence intervals constructed of least-square means (LSM) differences (Test minus Control) from the linear mixed models. The non-inferiority of the Test lens relative to the Control will be concluded if the upper confidence limit of LSM difference is below the non-inferiority margin 0.05 logMAR. The superiority will be established if the upper confidence limit is below 0.

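### The primary CLUE model does not analyse by the randomization stratum: no site-by-period term is planned, so any site differences in period change slightly widen the primary interval

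*Combined protocol and SAP*

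**What the plan says.** **Randomization (Section 5.1).** Subjects are assigned "using a 2×2 crossover design with 2 lens types and 2 periods", to Test/Control or Control/Test. "Randomization will be stratified by site", and "Each block will contain two different lens trial sequences". The number of sites and the allocation ratio are not stated.

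**Primary model (Section 14.5).** Apart from baseline, the fixed effects are listed as follows: "The model will include the experimental design factors: sequence of lens wear, period, lens type, time point and interaction between lens and time point". Correlation is handled within subject only: "The covariance between residual errors from the same subject across lens wearing periods/time point will be selected", from compound symmetry or unstructured. Neither site nor site-by-period is named. Non-inferiority is judged by whether the lower limit of the 95% interval lies above −5.

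**Secondary model (Section 14.6).** The fixed effects are "sequence of lens wear, lens wearing period, lens type, distance and the interaction between lens type and distance as fixed effects". It adds that "Site and subject nested in site will be included as random effects when appropriate". It has no site-by-period term either.

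**Analysis set (Sections 14.1 and 14.3).** All analyses use the per-protocol set, which is limited to subjects who completed every visit.

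**The concern.** An analysis normally reflects the factor used to stratify the randomization. Here the sequences are balanced within site, yet the primary model pools all subjects as if there were one stratum. If scores change from period 1 to period 2 by different amounts at different sites, blocking keeps those shifts largely out of the lens estimate, but the pooled model still counts them as error. The interval is then wider than the design warrants.

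Such shifts are conceivable. Period 1 includes fitting, modification partly at the investigator's discretion and an optimization visit, followed by 12±2 days with the final pair. Period 2 reuses the powers dispensed at Visit 2 with no optimization (Sections 4.1, 7.1 and 7.2). Site habits could therefore affect the period difference. This is a mechanism only; the documents give no estimate of such shifts. At stake is a little precision in a trial whose stated power is 0.48 at a true difference of zero.

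**Working it through.** **1. Difference SD.** The documents give no SD. Section 14.2 gives power of 0.48, 0.72 and 0.89 at true differences of 0, 2 and 4, with 50 subjects, margin −5 and type I error 0.05. For a paired non-inferiority test the noncentrality is (difference + 5) ÷ (SD/√50). With 48 df and one-sided 0.05, an SD of about 21.9 gives 0.479, 0.721 and 0.889, which matches all three rows. At one-sided 0.025 no single SD fits them (best fit 0.45, 0.73, 0.91). So 21.9 is an inferred value, tied to one-sided 0.05.

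**2. What a site main effect does.** Write a subject's score as site effect + period effect + lens effect + site-specific period effect + subject effect + error. In the period 1 minus period 2 difference, the site effect, the subject effect and the single Visit 1 baseline all drop out. The site-specific period shift remains. The standard error of the lens difference, computed by generalized least squares, confirms this:

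| Layout (sites × subjects) | No site term | Random site (variance 0, 100, 400) | Fixed site |
|---|---|---|---|
| 5 × 10 | 3.095 | 3.095 | 3.095 |
| 10 × 5 | 3.159 | 3.159 | 3.159 |
| 2 × 25 | 3.097 | 3.097 | 3.097 |

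The 14.6 site term would therefore leave the primary interval unchanged in complete pairs.

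**3. What site-by-period does, by formula.** Take 21.9 as the total SD, including any shifts. Assume k = 4 to 8 sites and site-to-site SD s of the period shift.

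- Without the term: t(48) × 21.9/√50 = 2.0106 × 3.097 = 6.23.
- With the term, fitted as fixed (worst case for df): t(48 − (k − 1)) × √(21.9² − s²)/√50.

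For k = 6, t(43) = 2.0167:

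| s | √(21.9² − s²) | Half-width | Change |
|---|---|---|---|
| 0 | 21.90 | 6.25 | +0.3% |
| 3 | 21.69 | 6.19 | −0.6% |
| 5 | 21.32 | 6.08 | −2.3% |
| 8 | 20.39 | 5.81 | −6.6% |

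At s = 0 the cost is +0.2% for k = 4 and +0.4% for k = 8. The formula slightly overstates the gain, because with few sites part of the shift variance is already absorbed by the overall period effect. Simulation with 5 sites and the same total SD gives about −2% at s = 5 and −6% at s = 8.

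**4. Interval behaviour, by simulation.** Here the shifts are added on top of an SD of about 21.9, with 5 sites of 10, true difference 0 and 4,000 runs per row. Each pair of figures is without / with site-by-period.

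| Shift SD | Empirical SE (both) | Mean half-width | Coverage | Non-inferiority power |
|---|---|---|---|---|
| 0 | 3.08 | 6.18 / 6.20 | 94.8% / 94.7% | 0.34 / 0.34 |
| 5 | 3.07 | 6.31 / 6.19 | 95.6% / 95.2% | 0.33 / 0.34 |
| 10 | 3.10 | 6.69 / 6.20 | 96.3% / 94.7% | 0.30 / 0.36 |
| 15 | 3.07 | 7.26 / 6.18 | 97.5% / 95.2% | 0.24 / 0.35 |

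The mean estimate stays within 0.1 of zero throughout, and its true standard error does not change with the shift. Only the model's estimate of that error is inflated. Power here is below 0.48 because the interval is two-sided 95% (one-sided 0.025), whereas the power table fits one-sided 0.05; that mismatch is a separate matter.

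**Simplification.** Steps 1 to 4 treat the 2-week comparison as one difference per subject and set aside the other time points in the 14.5 model.

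**The case against.** The strongest case for leaving 14.5 alone is this. The crossover already removes constant between-site differences, within-subject correlation is modelled, and the omission costs validity nothing: coverage is at or above nominal. Nothing in the documents shows that sites differ in period change, and if they do not, the extra term widens the interval slightly. Its variance would also be estimated from few sites. All of this stands. It limits the point to a small refinement but does not remove it, because the term costs almost nothing and it is how a 2×2 crossover is analysed by the strata it randomized within.

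A reader might infer four stronger things, which the documents do not support:

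- **That the discrepancy between 14.5 and 14.6 causes the loss.** It does not. The site effects in 14.6 are intercepts, included only conditionally, and they do not absorb period shifts. Consistency with 14.6 is no reason to add site-by-period, since 14.6 lacks it too.
- **That the omission biases the comparison or inflates false non-inferiority.** The error is in the conservative direction.
- **That incomplete pairs make site matter in the primary analysis.** The per-protocol set requires all visits. Incomplete pairs arise only in the multiple-imputation sensitivity analysis of Section 14.9, planned if dropout exceeds 15%.
- **That the term would rescue a half-width already above the margin.** At a shift SD of 8 the half-width is still about 5.8 against a margin of 5. Low power is a sample-size matter.

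**Conclusion.** The point holds as a minor one. The primary model does not analyse by the randomization stratum, and the term that would do so, site-by-period, is missing from both 14.5 and 14.6. The consequence is a slightly conservative interval if sites differ in their period change, and none if they do not. On an assumed 4 to 8 sites, 50 complete pairs, roughly 1:1 sequences and a back-solved difference SD of 21.9, adding the term changes the 95% half-width by about +0.2% to +0.4% with no shifts, −2% at a shift SD of 5 and −6% at 8. Larger shifts would cost more, but nothing in the documents suggests them. Confidence in the structural statement is high; confidence that the gain would be noticeable in this trial is low.

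**What to change.** In Section 14.5, pre-specify site and site-by-period as random effects, with site-by-period dropped if its variance is estimated as zero. For coherence, make the same addition in Section 14.6, where site alone is now conditional. If the sponsor prefers to leave the stratum out, one sentence should give the reason. Stating the planned number of sites would let a reader judge the cost.

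The change is SAP wording only and should be settled before unmasking. The price is a few degrees of freedom at most: even with the term fitted as fixed at 8 sites, 7 are lost (48 to 41) and the half-width grows by about 0.4% if sites do not differ.

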5.2. Masking

This is a double-masked study with the subjects and the investigators being masked.

Under normal circumstances, the mask should not be broken until all subjects have completed the study and the database is finalized. Otherwise, the mask should be broken only if specific emergency treatment/course of action would be dictated by knowing the treatment status of the subject. In such cases, the Investigator may, in an emergency, contact the medical monitor. In the event the mask is broken, the Sponsor must be informed as soon as

possible. The date, time, and reason for the unmasking must be documented in the subject record. The Investigator is also advised not to reveal the study treatment assignment to the clinical site or Sponsor personnel.

Subjects who have had their treatment assignment unmasked are expected to return for all remaining scheduled evaluations. Subjects who are discontinued may be replaced.

5.3. Procedures for Maintaining and Breaking the Masking

The test articles mask shall not be broken unless information concerning the lens type is necessary for the urgent medical treatment of a subject. The Sponsor must be notified before the mask is broken.

When dispensing test articles, the following steps should be followed to maintain randomization codes:

1. Investigator or designee (documented on the Delegation Log) will consult the lens fitting schedule/randomization scheme to obtain the test article assignment for that subject prior to dispensing
2. Investigator or designee will record the subject's number on the appropriate line of the randomization scheme if applicable
3. Investigator or designee will pull the appropriate test articles from the study supply. All test articles that are opened, whether dispensed (placed/fit on eye or dispensed outside the clinical site) or not, must be recorded on the Test Article Accountability Log in the "Dispensed" section

6. STUDY INTERVENTION

6.1. Identity of Test Articles

The following contact lenses will be used in this study:

Table 1: Test Articles

	Control	Test
Name	JJV Investigational Multifocal Contact Lens 1	JJV Investigational Multifocal Contact Lens 2
Manufacturer	Johnson & Johnson® Vision, Inc.	Johnson & Johnson® Vision, Inc.

Lens Material	senofilcon A	senofilcon A
Nominal Base Curve @ 22°C	8.35 mm	8.35
Nominal Diameter @ 22°C	14.3 mm	14.3
Nominal Distance Powers (D)	+1.00 D to +4.00 D in 0.25 D steps	+1.00 D to +4.00 D in 0.25 D steps
Nominal Cylinder Powers (D) and Axes	None	None
Nominal ADD Powers (D)	Low, Mid, High	Low, Mid, High
Water Content	38%	38%
Center Thickness	0.070 mm (-3.00 D)	0.070 mm (-3.00 D)
Oxygen Permeability (Dk)	122.0	122.0
Wear Schedule in Current Study	Daily Wear Reusable	Daily Wear Reusable
Replacement Frequency	Two Weeks	Two Weeks
Packaging Form (vial, blister, etc.)	Blister	Blister

6.2 Ancillary Supplies/Products

The following solutions will be used in this study:

Table 2: Ancillary Supplies

[figure not shown]
Solution		
Solution Name/Description	Eye-Cept® Rewetting Drops	OPTI-FREE® Replenish® Multipurpose Disinfecting Solution
Manufacturer	Optics Laboratory	Alcon Laboratories
Preservative	Non-Preserved	Myristamidopropyl dimethylamine 0.0005% polyquaternium-1 0.001%

6.3. Administration of Test Articles

Test articles will be dispensed to subject meeting all eligibility requirements, including any dispensing requirements set forth in this clinical protocol. Subjects will be dispensed an adequate supply of test articles to complete the study. Lost or damaged test articles may be replaced at the discretion of the Investigator and/or the Sponsor.

6.4. Packaging and Labeling

The test articles will be packaged in blisters, as the primary packaging. The test article will be over-labeled to mask the subject to the identity of the lens. The test articles will be in investigational cartons sealed with a tamper evident seal, commercial cartons, or in plastic bags as the secondary packaging form. The sample study label is shown below:

6.5. Storage Conditions

Test articles will be maintained at ambient temperatures at the clinical site. Test articles must be kept under secure conditions.

6.6. Collection and Storage of Samples

When possible, any lens or test article associated with an Adverse Events and/or a Product Quality Complaint must be retained and stored in a glass vial with moderate solution pending directions from the sponsor for potential return to JJV.

6.7. Accountability of Test Articles

JJV will provide the Investigator with sufficient quantities of study article and supplies to complete the investigation. The Investigator is asked to retain all lens shipment documentation for the test article accountability records.

Test article must be kept in a locked storage cabinet, accessible only to those assigned by the Investigator for dispensing. The Investigator may delegate this activity to authorized study site personnel listed on the Site Delegation Log. All test articles must be accounted. This includes:

1. What was dispensed for the subject for trial fitting, to wear out of the office, or issued for the subject to replace appropriately between visits
2. What was returned to the Investigator unused
3. The number and reason for unplanned replacements

The Investigator will collect all unused test articles from the subjects at the end of the subject's participation. Subject returned unused test articles must be separated from the clinical study inventory of un-dispensed test articles and must be labeled with the subject number and date of return. Following final reconciliation of test articles by the monitor, the Investigator or monitor will return all unused test articles to the Sponsor.

If there is a discrepancy between the shipment documents and the contents, contact the study monitor immediately.

Reference [REDACTED] Site Instructions for Test Article Receipt and Test Article Accountability for additional information

7. STUDY EVALUATIONS

7.1. Time and Event Schedule

Table 3: Time and Events

Visit Information	Visit 1 Screening, Baseline, Treatment 1	Visit 2 Treatment 1 Follow-up 1 Optimization	Visit 3 Treatment 1 Follow-up 2	Visit 4 Baseline Treatment 2 Fitting	Visit 5 Treatment 2 Follow-up 1
Time Point	Day 0	Day 3±1 from V1	Day 12±2 from V2 Complete 7±3 days washout before V4	Day 7±3 from V3 Day 0	Day 12±2 from V4
Estimated Visit Duration	2.5 hours	1.0 hour	1.5 hour	1.0 hour	1.5 hour
Statement of Informed Consent	x				
Demographics	x				
Medical History/Concomitant Medications	x				
Adverse Events and Concomitant Medications Review		x	x	x	x
Compliance		x	x		x
Habitual Contact Lens Information	x				
Contact Lens History	x				
Wear Time and Comfortable Wear Time with lenses	x	x	x		x
Screening Inclusion/Exclusion Criteria	x				
Subject Reported Ocular Symptoms	x	x	x	x	x
Baseline	x				

Visit Information	Visit 1 Screening, Baseline, Treatment 1	Visit 2 Treatment 1 Follow-up 1 Optimization	Visit 3 Treatment 1 Follow-up 2	Visit 4 Baseline Treatment 2 Fitting	Visit 5 Treatment 2 Follow-up 1
Time Point	Day 0	Day 3±1 from V1	Day 12±2 from V2 Complete 7±3 days washout before V4	Day 7±3 from V3 Day 0	Day 12±2 from V4
Estimated Visit Duration	2.5 hours	1.0 hour	1.5 hour	1.0 hour	1.5 hour
Questionnaire					
CLDEQ-8 Questionnaire	x		x		x
Distance and Near Entrance Visual Acuity					
x	x	x	x	x	x
Lens Removal	x	x	x	x	x
Keratometry	x				
Subjective Refraction and Distance Visual Acuity					
x					
Near ADD Determination	x				
Ocular Dominance	x				
ADD Refinement	x				
Near Visual Acuity	x				
Biomicroscopy	x	x	x	x	x
Baseline Inclusion/ Exclusion Criteria	x				
Continuance				x	
Lens Selection	x	x(If modified)		x	
Lens Insertion	x	x		x	
10 Minute Settling		x		x	
x		x		x	
Visual Satisfaction / Subjective	x	x	x	x	x

Visit Information	Visit 1 Screening, Baseline, Treatment 1	Visit 2 Treatment 1 Follow-up 1 Optimization	Visit 3 Treatment 1 Follow-up 2	Visit 4 Baseline Treatment 2 Fitting	Visit 5 Treatment 2 Follow-up 1
Time Point	Day 0	Day 3±1 from V1	Day 12±2 from V2 Complete 7±3 days washout before V4	Day 7±3 from V3 Day 0	Day 12±2 from V4
Estimated Visit Duration	2.5 hours	1.0 hour	1.5 hour	1.0 hour	1.5 hour
Acceptance					
Study Lens					
Distance and Near Visual Acuity	x	x	x	x	x
Distance Over Refraction and Visual Acuity	x	x		x	
Subjective Lens Fit Assessment	x	x	x	x	x
Binocular Over Refraction			x		x
Visual Performance			x		x
Modifications	x	x			
Post-Fit PRO Questionnaire	x	x		x	
PRO Questionnaire	x		x		x
Distance and Near Exit Visual Acuity	x	x	x	x	
Dispensing Criteria	x	x		x	
Instructions	x	x	x	x	
Schedule Follow-up	x	x	x	x	
Final Evaluation					x

7.2. Detailed Study Procedures

VISIT 1

Subjects must report to the visit wearing their habitual contact lenses to accurately assess baseline PRO (CLUE) performance. If the subject is not wearing their lenses they must be rescheduled.

Visit 1: Screening		
Step	Procedure	Details
1.1	Statement of Informed Consent	Each subject must read, understand, and sign the Statement of Informed Consent before being enrolled into the study. The Principal Investigator or his/her designee conducting the informed consent discussion must also sign the consent form. Note: The subject must be provided a signed copy of this document.
1.2	Demographics	Record the subject's age, gender, race and ethnicity.
1.3	Medical History and Concomitant Medications	Questions regarding the subjects' medical history and concomitant medications.
1.4	Habitual Lenses	Questions regarding the subject's habitual lens type and parameters.
1.5	Contact Lens History	Record the subject's correction type (i.e. monovision, multifocal, sphere with readers, etc.).
1.6	Wear time and Comfortable Wear time with Habitual lenses	Record the subjects wear time and comfortable wear time with their habitual contact lenses.
1.7	Eligibility after Screening	All responses to Screening Inclusion Criteria questions must be answered "yes" and all responses to Exclusion Criteria must be answered "no" for the subject to be considered eligible.

Visit 1: Baseline		
Step	Procedure	Details
1.8	Baseline PRO and CLDEQ-8 Questionnaires	The subject will evaluate the vision characteristics, comfort characteristics, handling characteristics, and visual symptoms of their habitual lenses using the PRO questions.
1.9	Ocular Symptoms	Subjects will respond to a verbal open-ended symptoms questionnaire.

1.10	Entrance Visual Acuity	
Distance and near Snellen visual acuity will be measured for each eye with the subject's habitual contact lenses in place.
 
For near measures use the ETDRS 2000 Series Chart 1 or 2. The acuity will be recorded to the nearest letter OD, OS and OU.
	████████
1.11	Lens Removal	Have the subject remove their habitual lenses and store in an approved storage solution.	████████
1.12	Keratometry	Keratometry will be performed OD and OS and the steep and flat dioptic power and corresponding meridians recorded.	████████
1.13	Subjective Refraction and Distance Visual Acuity	
An optimal, binocular balanced distance spherocylindrical refraction will be performed. Record the refraction and distance visual acuity to the nearest letter.
 
Note: Best distance visual acuity with spherocylindrical refraction must be at least 20/20⁻³ in each eye for the subject to be eligible in the study.
	████████
1.14	Near ADD Determination	The near reading addition will be determined using the binocular crossed cylinder technique (BCC) at 40 cm followed by optimization in a trial frame in step 1.16 below.	████████
1.15	Ocular Dominance	Determine the distance ocular dominance with the best distance correction in place using a +1.00-blur test. If the results are equivocal use the sighting dominance test to determine the dominant eye used for the study.	Appendix F
1.16	ADD Refinement	Place the BCC result in the trial frame and refine the near prescription with trial lenses (or flippers) under binocular conditions.	████████
1.17	Near Visual Acuity	Using the ETDRS 2000 Series Chart 1 or 2 near card placed at 40 cm. Record the near visual acuity OD, OS and OU at 40 cm.	████████
1.18	Biomicroscopy	
FDA Slit Lamp Classification Scale will be used to grade the findings and determine eligibility.
 
For the conjunctival redness █████ 0.5 unit increments will be used in the grading. Corneal Staining Assessment █████ will be graded in 1.0 increments.
 
If any of these slit lamp findings are Grade 3 or higher, the subject will be discontinued. If
	████████ ████████ ████████

		
discontinued a final examination must be completed.
 
If the clearance of the fluorescein needs to be expedited, preservative-free rewetting drops or saline may be instilled.
	
1.19	Eligibility after Baseline	
All responses to Inclusion Criteria questions must be answered “yes” and all responses to Exclusion Criteria questions must be answered “no” for the subject to be considered eligible. If so, proceed to lens fitting. If not, complete the final evaluation and discharge the subject.
	

Visit 1: Treatment 1 Lens Fitting			
Step	Procedure	Details	
1.20	Randomization	Record the randomization ID.	
1.21	Lens Selection	Select the lens pair and power based on the randomization scheme, spherical equivalent refraction and fitting guide for each eye. Record the Test lens parameters (power and lot number).	Appendix G (Fitting Guide)
1.22	Lens Insertion	
Subjects will insert the lenses themselves. If the lens is uncomfortable, inspect for damage and remove, reinsert or replace as necessary.
 
Damaged lenses will be stored in labeled vial with sterile saline, and clearly differentiated from the other worn lenses that will be shipped back to the Sponsor. Complete the Quality Product Complaint form.
	
1.23	Lens Settling	Allow the study lenses to settle for a minimum of 10 minutes.	
1.24	Determine Visual Satisfaction	Determine if the subject’s vision is acceptable with the lenses. Allow the subject to look down a hallway or out of a window for distance vision assessments, and for them to read a book, magazine or similar for near vision.	
1.25	Study Lens Distance and Near Visual Acuity	
Measure the distance and near visual acuity OD, OS and OU. Record the results.
 
Note: Use the ETDRS 2000 Series Chart 1 or 2 near card placed at 40 cm to measure the Near visual acuity
	
1.26	Distance Over-	Perform a distance over-refraction OD and OS	

	Refraction and Distance Visual Acuity	using loose lenses outside of the phoropter under ambient room illumination. The distance over-refraction may also be refined under binocular conditions. Record the results. The results of the distance over-refraction may also be checked for the impact on near vision under monocular and/or binocular conditions.	
1.27	Subjective Lens Fit Assessment	
Evaluate and grade lens centration, primary gaze movement, upgaze movement and tightness (push-up test).
 
 • The subject should not proceed to wear the lenses if any of the following is observed: • presence of limbal exposure (appearance of clear cornea) in any gaze • presence of edge lift • presence of unacceptable movement (excessive or insufficient) in all three movement categories (primary gaze, upgaze, and push-up). 
If either lens is deemed unacceptable, the subject will be discontinued from the study. Remove the lenses, perform a slit-lamp evaluation, and complete the Final Evaluation form.
	[REDACTED]
1.28	Modifications	
If the subject reports unsatisfactory vision or is unable to obtain 20/30 distance visual acuity OU with the lenses, then a modification must be attempted. If the subject reports satisfactory vision with the lenses a modification is not required, however at the Investigator's discretion and based upon their findings on the measured visual acuity and/or over- refraction the investigator may make a modification. Up to two attempts at modification are permitted if necessary, in order to achieve an acceptable distance and near binocular performance for the subject, and to enable them to wear that particular lens type. Follow the fitting guide allowing for at least 10 minutes of settling time between each lens modification attempted.
 
If modifications are required steps 1.21-1.27 will be repeated for each modification.
	Appendix G (Fitting Guides)
1.29	PRO Post-Fit	The subject will evaluate the vision	

	Questionnaire	characteristics, comfort characteristics, handling characteristics, and visual symptoms of the study lenses using the PRO questionnaire.	
1.30	Distance and Near Exit Visual Acuity	
Distance and near Snellen visual acuity will be measured for each eye with the study contact lenses in place.
 
For near measures use the ETDRS 2000 Series Chart 1 or 2. The acuity will be recorded to the nearest letter OD, OS and OU.
 
Note: The distance visual acuity must be at least 20/30 OU for the lenses to be dispensed.
	[REDACTED]
1.31	Dispensing Criteria	
The lenses will be dispensed for 2-4 days.
 
 • Distance Snellen acuity equal to or better than 20/30 OU • Subject must indicate that the vision is acceptable. • Subject must indicate that the comfort of the lenses is acceptable. • Lenses must have an acceptable general lens fit. 	
1.32	Patient Instructions	
Instruct the Subject the following:
 
 • The lenses will be worn on a daily wear basis. • OPTI-FREE® Replenish® solution will be used in a rub regime to disinfect and store the lenses each night in the lens case provided. • If determined necessary by the Investigator sterile non-preserved rewetting drops may be dispensed to be used as needed for dryness. • Subjects will be instructed to wear lenses for a minimum of 6 hours a day, every day during the study. • Subjects will be instructed to wear their glasses when not wearing the study lenses. • A patient instruction booklet will be provided. 
Note: In the event a lens is lost or damaged,
	

		the subject will return to the investigator site for replacement. As much as reasonably possible, a damaged lens should be returned to the investigational site and then returned to the Sponsor. If lens damage is present, complete the Product Quality Complaint Form. The lens will be stored in labeled vial with sterile saline and returned to the Sponsor.	
1.33	Schedule Follow-up	
The subject will be scheduled to return for their follow-up appointment in 3±1 day.
 
Note: To count the follow-up visit as a day of wear the Subject must have worn the study lenses for 6 hours prior to the visit.
	

VISIT 2

The subjects must present to Visit 2 wearing the study lenses. To be counted as a day of wear the lenses need to have been worn for at least six (6) hours prior to the visit.

Visit 2: Treatment 1 Follow-up 1			
Step	Procedure	Details	
2.1	Adverse Events and Concomitant Medications Review	
Review the subject's concomitant medications and record any changes from the previous study visit.
 
Record any adverse events or medical history changes from the previous study visit.
	
2.2	Wear Time	Record the hours the subject has worn the study lenses and the comfortable wear time on the day of follow-up.	
2.3	Compliance	
Record the subject's compliance with wearing the study lenses.
 
Note: Subjects must have worn lenses for at least 6 hours per day To be counted as a day of wear at this visit the Subject must have worn the study lenses for 6 hours prior to the visit.
	
2.4	Ocular Symptoms	Subjects will respond to a verbal open-ended symptoms questionnaire.	
2.5	Subjective Acceptance	Record whether the subjects distance and near vision with the lenses is acceptable.	
2.6	Distance and Near Entrance Visual Acuity	Measure the distance and near visual acuity OD, OS and OU. Record the results.	

		Note: Use the ETDRS 2000 Series Chart 1 or 2 near card placed at 40 cm to measure the Near visual acuity	
2.7	Distance Over- Refraction and Distance Visual Acuity	Perform a distance over-refraction OD and OS using loose lenses outside of the phoropter under ambient room illumination. The distance over-refraction may also be refined under binocular conditions. Record the results and distance visual acuity OD and OS. The results of the distance over-refraction may also be checked for the impact on near vision under monocular and/or binocular conditions.	
2.8	Determination of Lens Optimization	If the subject reports unsatisfactory vision or is unable to obtain 20/30 distance visual acuity OU with the lenses, then a modification must be attempted. If the subject reports satisfactory vision with the lenses a modification is not required, however at the Investigator's discretion and based upon their findings on the measured visual acuity and/or over- refraction the investigator may make a modification. Up to two attempts at modification are permitted if necessary, in order to achieve an acceptable distance and near binocular performance for the subject, and to enable them to wear that particular lens type. Follow the fitting guide and steps 1.21-1.27 in Visit 1 Fitting allowing for at least 10 minutes of settling time between each lens modification.	Appendix G (Fitting Guide)
2.9	Lens Fit Assessment:	Evaluate and grade lens centration, primary gaze movement, upgaze movement and tightness (push-up test). 
 • The subject should not proceed to wear the lenses if any of the following is observed: • presence of limbal exposure (appearance of clear cornea) in any gaze • presence of edge lift • presence of unacceptable movement (excessive or insufficient) in all three movement categories (primary gaze, upgaze, and push-up). 
If either lens is deemed unacceptable, the
	

		subject will be discontinued from the study. Remove the lenses, perform a slit-lamp evaluation, and complete the Final Evaluation form.	
2.10	Lens Removal	The study lenses will be removed and discarded.	
2.11	Biomicroscopy	
Perform biomicroscopy OD and OS. Slit Lamp Classification Scales will be used to grade the findings.
 
For the conjunctival redness [REDACTED] 0.5 unit increments will be used in the grading.
 
Corneal Staining Assessment [REDACTED] will be graded in 1.0 increments.
 
If the clearance of the fluorescein needs to be expedited, preservative-free rewetting drops or saline may be instilled.
	[REDACTED] [REDACTED] [REDACTED]
2.12	Insertion of Study Lenses	Dispense the subject a new pair of lenses that match the distance and ADD power of the lenses that were removed in Step 2.12 above.	
2.13	PRO Post-Fit Questionnaire	The subject will evaluate the vision characteristics, comfort characteristics, handling characteristics, and visual symptoms of the study lenses using the PRO questionnaire.	
2.14	Distance and Near Exit Visual Acuity	
Distance and near Snellen visual acuity will be measured for each eye with the study contact lenses in place.
 
For near measures use the ETDRS 2000 Series Chart 1 or 2. The acuity will be recorded to the nearest letter OD, OS and OU.
 
Note: The distance visual acuity must be at least 20/30 OU for the lenses to be dispensed.
	[REDACTED]
2.15	Dispensing Criteria	
The lenses will be dispensed for 12 ± 2 day.
 
 • Distance Snellen acuity equal to or better than 20/30 OU • Subject must indicate that the vision is acceptable. • Subject must indicate that the comfort of the lenses is acceptable. • Lenses must have an acceptable general lens fit. 	
2.16	Patient Instructions	Instruct the Subject the following:	

		
 • The lenses will be worn on a daily wear basis. • OPTI-FREE® Replenish® solution will be used in a rub regime to disinfect and store the lenses each night in the lens case provided. • If determined necessary by the Investigator sterile non-preserved rewetting drops may be dispensed to be used as needed for dryness. • Subjects will be instructed to wear lenses for a minimum of 6 hours a day, every day during the study. • Subjects will be instructed to wear their glasses when not wearing the study lenses. • Subjects will be instructed to bring their habitual contacts or spectacles to the next visit. 
Note: In the event a lens is lost or damaged, the subject will return to the investigator site for replacement. As much as reasonably possible, a damaged lens should be returned to the investigational site and then returned to the Sponsor. If lens damage is present, complete the Product Quality Complaint Form. The lens will be stored in labeled vial with sterile saline and returned to the Sponsor.
	
2.17	Schedule Follow-up	
The subject will be scheduled to return for their follow-up appointment in 12±2 days.
 
Note: To count the follow-up visit as a day of wear the Subject must have worn the study lenses for 6 hours prior to the visit.
	

VISIT 3

The subjects must present to Visit 3 wearing the study lenses. To be counted as a day of wear the lenses need to have been worn for at least six (6) hours prior to the visit.

Visit 3: Treatment 1 Follow-up 2		
Step	Procedure	Details
3.1	Adverse Events and Concomitant Medications Review	
Review the subject's concomitant medications and record any changes from the previous study visit.
 
Record any adverse events or medical history changes from the previous study visit.

3.2	Wear Time	Record the hours the subject has worn the study lenses and the comfortable wear time on the day of follow-up.
3.3	Compliance	
Record the subject's compliance with wearing the study lenses.
 
Note: Subjects must have worn lenses for at least 6 hours per day
 
To be counted as a day of wear at this visit the Subject must have worn the study lenses for 6 hours prior to the visit.

3.4	PRO and CLDEQ-8 Questionnaires	The subject will evaluate the vision characteristics, comfort characteristics, handling characteristics, and visual symptoms of the study lenses using the PRO questionnaire.
